3.1 Study Goals

- 1) To determine whether consumption of micronutrient enriched MEC products from 8-14 weeks' gestation to delivery improves birth length in the intervention compared to the placebo group (Phase 1);
- 2) To determine if the daily consumption of micronutrient enriched crackers (MEC) by pregnant mothers from 8-14 weeks' gestation to 5 months post-partum improves attained linear growth of infants at age 5 months and linear growth velocity of infants from birth to age 5 months in the intervention compared to the placebo group (Phase 2).

3.2 Secondary Outcomes

- 1) To determine the birth weight (measured within 24 hours after delivery);
- 2) To determine the maternal hemoglobin levels at 35-36 weeks' gestational age and 5 months post-partum (± 1 week);
- 3) To determine the maternal food intake at 35-36 weeks' gestational age, and 2 months post-partum (± 1 week), and 5 months post-partum (± 1 week);
- 4) To determine the breast milk volume and micronutrient breast milk concentrations at 5 months' post-partum (± 1 week);
- 5) To determine the infant breast milk micronutrient intake, based on breast milk volume and micronutrient breast milk concentrations at 5 months' post-partum (± 1 week);
- 6) To determine maternal micronutrient status (ferritin, transferrin serum, RBP, zinc, and selenium of mother at 35-36 weeks' gestational age and 5 months' post-partum (± 1 week), after being adjusted with the inflammation status (C-reactive protein and alpha-1-acid glycoprotein);

- 7) To determine infant micronutrient status (ferritin, transferrin serum, retinol-binding protein RBP, zinc, and selenium at 5 months old (\pm 1 week), after being adjusted with the inflammation status (C-reactive protein and alpha-1-acid glycoprotein);
- 8) To determine the infant development at 2 and 5 months old (\pm 1 week) in the intervention and control groups;
- 9) To determine the morbidity incidence rate of the mothers and infants in the intervention and control groups.

4. Data Management and Analyses

4.1 Data Management

Enumerators will daily double-check the accuracy and completeness of data collected. All data will be doubly entered and checked daily for identical entries. Data cleaning will be conducted weekly by the data manager to ensure values are within the acceptable/plausible ranges and identify any missing values. Any errors will be flagged and re-checked with hard copy data.

4.2 Statistical Analysis

Primary analyses will be by intention to treat. The mean number of crackers consumed overall and compliance rates will be examined. Only live born infants will be included in all analyses. Intervention groups will be compared using mixed effect regression models using cluster (village) as a random effect. Main outcomes for analyses for phase 1 are birth length and for phase 2 are attained and incremental linear growth at 5 months post-partum. Analyses for phase 2 will be conducted with adjustment for weight-for-age and breastfeeding practice (exclusively/partially breastfeeding), where appropriate. Model assumptions will be checked using standard procedures and variables log transformed when necessary. Guidelines for reporting will be followed, as outlined in the Consolidated Standards of Reporting Trials (CONSORT) statement: extension to cluster randomised trials.

Given the short period of data collection and the anticipation that no highly potential harm/risks will be expected, the study will continue until the end of data collection without data interim analysis. As the data will not be analysed until the whole study is complete, there is no requirement to power the study for multiple looks. The research team will report

any undesirable events to the DSMB and the Ethics Committee. DSMB may call for an interim analysis if it is required. Termination of the clinical trial will be carried out based on the recommendation from the DSMB and/or Ethics Committee.

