2.4 Population and Sample

2.4.1 Inclusion and Exclusion Criteria

1) Inclusion Criteria

- a. Pregnant women aged 19-35 years old;
- b. Gestational age 7-13 weeks at the time of the screening process and be willing to take part in an intervention study at 8-14 weeks gestation;
- c. Permanent residents who will stay in the research area for the following 1 year.

2) Exclusion Criteria

- a. Mothers who have chronic diseases such as hypertension (blood pressure \geq 140/90 mmHg) or under treatment for hypertension, diabetes (non-fasting blood sugar when >200 mg/dL) or under treatment for diabetes, hypercholesterolemia (blood total cholesterol >240 mg/dL), hyperuricemia (blood uric acid > 6 mg/dL), have had a history of tuberculosis or under treatment for tuberculosis or under treatment for other chronic diseases that requires a long treatment, such as cancer, heart disease, epilepsy, etc.;
- b. Have a history of preeclampsia/eclampsia and gestational diabetes in their previous pregnancy;
- c. Have a risk of chronic energy deficiency (mid-upper arm circumference < 23.5 cm);
- d. Have severe anemia (hemoglobin < 70 g/L);
- e. Have a history of allergy to chicken liver and/or eggs.

3) Drop-out criteria

- a. Preeclampsia, eclampsia;
- b. Dead infant/stillbirth;
- c. Twin delivery;
- d. Infants are born with congenital anomalies;
- e. Infants are not breastfed.

4) Other criteria

If an infant is born with Low Birth Weight (LBW) or is premature, then the infant will not be included in the measurement of breast milk volume and

assessment of exclusive breastfeeding status with Deuterium Oxide Dose-to-Mother Technique. However, the growth and data collection such as anthropometry and ages and stages questionnaires (ASQ-3) will still be carried out.

[figure not shown]

Figure 1 Study designs. MEC: Micronutrient-enriched Crackers.

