2.4.2 Population and Sample size calculation

The population of this study are the people who live in the area of Pamulihan, Sukasari and Tanjungsari Sub-Districts, Sumedang District, West Java. All parameters used in calculating sample sizes can be seen in Table 1. Design effects, cluster/village, are estimated using previous data collected in the same area.

- 1) Phase 1: To detect a 1 cm difference in birth length between the intervention and control groups (this is approximately 0.5 SD from the WHO Growth Chart (2007)), with power of 0.90, statistical significance of 0.05, and design effect of 1.1 due to village clusters, a minimum sample size of 228 is required (114 in each group) (to be presented in tabular form).
- 2) Phase 2: Based on an average growth velocity of 3-3.2 cm/month, and to detect differences in growth velocity of 0.70 cm between the intervention and control groups, with power of 0.80, statistical significance of 0.05, assuming a standard deviation of 2.2 cm/month, a within-person correlation of 0.73 and a design effect of 1.1 due to village clusters, a sample size of 162 would be required (81 in each group) (to be presented in tabular form).

As the primary outcomes for Phase 1 require a sample size of 228, then 11 participants from 22 clusters will be required. However, we aim to recruit 11 participants from 28 clusters, giving a sample size of 308. This will allow for exclusion due to stillborn or premature birth (~10%, i.e., n~15 in each group) and drop-out or loss-to-follow-up of approximately 15%, so the total sample size is 324. For Phase 2, if 231 participants are retained, a further 1-5% may fail to breastfeed their infants, giving a final sample size of 219-228 to assess Phase 2 outcomes. This sample size will also permit the detection of the differences in the secondary outcomes also specified below (Table 2), in addition to the primary outcomes.

Table 2. Parameters used in calculating sample sizes for secondary outcomes

Measure	Observed mean	Observed SD	Difference to detect	ICC	Design effect	Sample size**
Birth length (cm) ^a	49.7	2.2	1.0	0.010	1.10	114
Infant length at 5 months (cm) ^a	63.0	2.2	1.0	0.010	1.10	114
Birth weight (g) ^a	3013	514	200	0.010	1.10	116
Haemoglobin at 3 rd trimester (g/dL) ^b	12.6	1.2	0.5	0.048	1.48	132
Volume of breast milk at 5 months post-partum (mL/day) ^c	787	148	70	0.010	1.10	80
Micronutrient concentrations of breast milk at 5 months post-partum (Vit A, µg/L) ^c	634	281	130	0.036	1.36	102

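### The SAP promises intention to treat among live births, but its drop-out list and sample-size count leave non-breastfed infants out of the Phase 2 primary outcomes

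*SAP*

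**What the plan says.** Four places in the SAP bear on who is analysed in Phase 2.

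- **Section 4.2 (analysis).** The principle is "Primary analyses will be by intention to treat". The only restriction given is "Only live born infants will be included in all analyses". The Phase 2 main outcomes are attained and incremental length at 5 months.
- **Section 2.4.1, item 3 (drop-out criteria).** The fifth criterion is "Infants are not breastfed".
- **Section 2.4.2 (sample size).** Starting from 231 retained participants, the text continues: "a further 1-5% may fail to breastfeed their infants, giving a final sample size of 219-228 to assess Phase 2 outcomes".
- **Section 4.2 (covariates).** Phase 2 analyses are to be run with "adjustment for weight-for-age and breastfeeding practice (exclusively/partially breastfeeding), where appropriate".

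On premature birth, section 2.4.2 describes the recruitment margin with the words "This will allow for exclusion due to stillborn or premature birth (~10%, i.e., n~15 in each group". Section 2.4.1, item 4, takes premature and low-birth-weight infants out of the breast-milk volume and exclusive-breastfeeding assessment only, and continues their anthropometry.

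**The concern.** The analysis section would analyse every live-born infant as randomised. The drop-out list and the sample-size count point to a smaller Phase 2 group, selected on whether the infant was breastfed. Two analysts working from different sections could analyse different infants for a primary outcome.

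The selection matters because of when it happens. Breastfeeding is settled after randomisation, and the trial itself treats lactation as something the product may change: breast-milk volume is a secondary outcome (section 3.2), with a 70 mL/day difference to detect (Table 2). If the product affects whether mothers breastfeed, the infants left in the two arms are no longer comparable by virtue of randomisation.

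Adjusting for breastfeeding practice raises the same difficulty. So does adjusting for infant weight-for-age if it is measured after birth. The SAP does not say when weight-for-age is measured.

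**Working it through.** **1. Reproduce the plan's count.** Inputs from section 2.4.2: 28 clusters of 11, about 10% stillborn or premature, about 15% drop-out or loss to follow-up, and 1-5% not breastfeeding.

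- Recruited: 28 × 11 = 308.
- Retained: 308 × (1 − 0.10 − 0.15) = 231, as stated.
- After the breastfeeding subtraction: 231 × 0.95 = 219.45 and 231 × 0.99 = 228.69, matching the stated 219-228.
- Infants counted out: 231 − 228 = 3 to 231 − 219 = 12.

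The same paragraph also gives a total of 324. Since 324 × 0.75 = 243, the 231 rests on 308.

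**2. Is this ordinary attrition?** The 15% for drop-out and loss is already spent in reaching 231. The further 1-5% comes off participants described as retained, and the reason given is failure to breastfeed, not a missing measurement.

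**3. Is it confined to breast-milk outcomes?** The 219-228 is given for Phase 2 outcomes without limit. The next sentence of section 2.4.2 brings in the secondary outcomes as additional to the primary ones. Sections 3.1 and 4.2 make 5-month length and growth velocity the Phase 2 primary outcomes.

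**4. The covariate.** With two levels, exclusive and partial, a non-breastfed infant has no valid value. A model that includes the covariate would drop such an infant even if length had been measured.

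**5. What a removal could do.** If *k* of *n* infants in one arm are removed and their mean length differs by *D* from the rest of that arm, the arm mean moves by *D* × *k*/*n*. With *n* = 231/2 = 115.5 and all removals in one arm, *k*/*n* is 3/115.5 = 0.026 to 12/115.5 = 0.104, so about 0.03-0.10 cm for each 1 cm of *D*. The SAP gives neither *D* nor the split by arm. This is therefore a conversion factor, not an estimate of bias. If numbers and differences are equal in both arms, the effect on the comparison is zero.

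**6. Power.** For a 1.0 cm difference in 5-month length, with SD 2.2 and design effect 1.1 (Table 2) and two-sided alpha 0.05 (two-sided is assumed):

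power = Φ( 1 / (2.2 × √(2 × 1.1/(N/2))) − 1.96 )

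| N | Power |
|---|---|
| 219 | 0.894 |
| 228 | 0.905 |
| 231 | 0.909 |

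For velocity (0.70 cm, SD 2.2, correlation 0.73, design effect 1.1), the baseline-adjusted formula at 80% power gives 2 × (2.2 × (1.960 + 0.842)/0.7)² × (1 − 0.73²) × 1.1 = 79.7, or 80 per group against the stated 81. Power at 219-231 is then 0.907-0.921.

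**The case against.** The strongest reply is that no analysis rule removes non-breastfed infants. The drop-out list may describe study conduct, and section 2.4.2 is a planning allowance. The only stated analysis rule is intention to treat among live births. If drop-outs are simply not measured at 5 months, the result is missing outcome data, which can coexist with intention to treat.

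Much of this stands. A reader might infer that the SAP prescribes deleting these infants from the analysis. It does not say so; the removal is inferred from a drop-out criterion and a count. What survives is that the count is expressly for the Phase 2 outcomes, is taken from participants already retained, and agrees with the drop-out criterion. The sections conflict and need reconciling.

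Three other readings are tempting and are not supported:

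- **A sample-size shortfall.** Table 2 lists 114 per group for 5-month length, which 219-228 reaches only at its top end. But the table's footnote sets that column at 80% power, where 2 × 2.2² × (1.960 + 0.842)² × 1.1 = 83.6, or 84 per group (168 in total). The 114 corresponds to about 90% power: 2 × 2.2² × (1.960 + 1.282)² × 1.1 = 111.9. So 219 is ample for the power the table states.
- **Premature infants lost from the birth-length analysis.** Only the allowance in section 2.4.2 calls premature birth an exclusion. Sections 2.4.1 (item 4) and 4.2 keep premature live births, so no analysis is changed.
- **Exclusion of live births with preeclampsia, twinning or anomalies.** These share the drop-out list, but section 2.4.2 does not subtract them by name from the Phase 2 number, and section 4.2 would include them.

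**Conclusion.** The point holds as a conflict between sections 2.4.1, 2.4.2 and 4.2 over the Phase 2 primary analysis set, and it should be fixed before analysis. It concerns about 3-12 of 231 infants (1-5%), taking the plan's own base of 308 recruited and its own loss rates.

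The risk is bias from selecting or adjusting on something determined after randomisation. That risk depends on breastfeeding differing by arm, or on non-breastfed infants differing in length unequally between arms. The SAP gives no figures on either, so size and direction are unknown and may be zero. Power stays close to 0.90 for 5-month length whichever count is used, and it is not part of the case. The wording on premature birth and the two recruitment totals are minor matters of consistency.

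**What to change.** - **Primary set.** Reconcile sections 2.4.1, 2.4.2 and 4.2 by defining the Phase 2 primary set as all live-born infants with a length measurement, analysed by allocated village regardless of breastfeeding status. State that length data held for infants meeting a drop-out criterion are included.
- **Primary model.** Fit it without breastfeeding practice and without infant weight-for-age measured after birth. Move both adjustments to secondary analyses, with a level for non-breastfed infants.
- **Sensitivity.** Report a breastfed-only set as a sensitivity analysis, with removals by arm.
- **Section 2.4.2.** Remove the non-breastfed subtraction for the growth outcomes. As minor notes, reconcile the mention of premature birth in the exclusion allowance with sections 2.4.1 and 4.2, and reconcile 308 with 324 before restating any N.

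The analysis changes are a matter of SAP wording. The limit is data: infants not measured at 5 months remain missing whatever the set is called, and measuring non-breastfed infants may need an arrangement in the protocol, which is not shown. Whether meeting a drop-out criterion should stop the product is a clinical matter and is not addressed here.

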2.1 Brief Description

The design of this study is a double-blind two-phase cluster randomized controlled trial to examine the effect of daily consumption of locally produced MEC (intervention group) compared to placebo crackers (control groups) in two time intervals: 1) from the second trimester of pregnancy (8-14 weeks) to delivery only; and 2) when the intervention is continued for up to 5 months post-partum, with the primary outcomes being birth length, attained linear growth, and growth velocity of the infant.

A total of 28 clusters (villages) will be randomised to either intervention or control using a randomized sequence. Selected pregnant women from these villages will receive daily interventions in the form of 7 x 75 gram micronutrient-enriched food products, made from basic ingredients of liver and chicken eggshells (Micronutrient-enriched Crackers/MEC) or placebo. The research team will give 100 grams of the same product as the respondents to the family of the respondents, so the respondents will not need to share the intervention product with the other family members. MEC or placebo will be produced locally and be identical in size, color, and packaging. MEC or placebo packages will be coded and only the production manager will know the allocated codes for the MEC or placebo packages. The production manager will be instructed to not share the code with any of the investigators involved in the trial until the primary outcomes of the study have been analyzed statistically or as requested by the Ethics Committee and/or Data Safety Monitoring Board (DSMB).

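### The live-born restriction covers all analyses and the drop-out criteria have no stated analysis consequence, so read literally, serious pregnancy harms can fall out of the secondary comparisons uncounted by arm

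*SAP*

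**What the plan says.** Section 4.2 sets two rules on who is analysed. The first is "Primary analyses will be by intention to treat", which is not extended to the secondary outcomes. The second is "Only live born infants will be included in all analyses", which is not limited to infant outcomes.

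Section 2.4.1 lists five drop-out criteria: (a) preeclampsia or eclampsia; (b) "Dead infant/stillbirth"; (c) twin delivery; (d) "Infants are born with congenital anomalies"; and (e) an infant who is not breastfed. It does not say whether a drop-out stops the product, stops follow-up or leaves the analysis.

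Section 3.2 names as secondary outcome 9: "To determine the morbidity incidence rate of the mothers and infants in the intervention and control groups". Other secondary outcomes are purely maternal and are measured before delivery as well as after it: haemoglobin, food intake and micronutrient status at 35-36 weeks' gestation.

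On safety, section 4.2 says the team will report "any undesirable events to the DSMB and the Ethics Committee". It plans no interim analysis, though the DSMB may ask for one.

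**The concern.** Stillbirth and preeclampsia occur during follow-up, and a product eaten daily in pregnancy could in principle affect them in either direction. An anomaly may already be present at intake, but it is found afterwards and is a usual item of pregnancy safety reporting. Here these events serve as reasons for leaving the trial, and the plan does not also make them results.

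The conflict is sharpest for outcome 9. Preeclampsia is maternal illness, so it belongs in that comparison, yet criterion (a) makes it a ground for drop-out and nothing says it is counted first. A similar problem affects a woman measured at 35-36 weeks whose infant is later stillborn. Her data are valid maternal data, but a rule covering all analyses can be read as removing them.

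At stake is what the final report can say about harm. Since no interim look is planned, the final analysis is the only planned comparison between arms. It names none of these events. Two analysts following the text could also build different populations for outcome 9.

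**Working it through.** **1. What each rule reaches.** This sets the live-born sentence (4.2) against the drop-out list (2.4.1) and the outcome list (3.2).

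| Event | Reached by the live-born sentence? | Drop-out criterion | Comparison by arm named? |
|---|---|---|---|
| Stillbirth, as an infant event | Yes, in every analysis | b | No |
| Maternal outcomes of a woman with a stillbirth | Only if the sentence extends to maternal analyses | b | Maternal outcomes are planned; her inclusion is unclear |
| Preeclampsia or eclampsia with a live birth | No | a | Not named; fits outcome 9, counting not stated |
| Anomaly in a live-born infant | No | d | No |
| Death after live birth | No | b | No |

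Only the first row follows directly from the live-born sentence. The second depends on its scope. The other three depend on what drop-out means for the analysis.

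**2. What drop-out appears to mean.** Section 2.4.2 gives evidence through its arithmetic.

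- Inputs: 28 clusters x 11 women = 308; about 10% excluded for stillbirth or prematurity (about 15 per group); about 15% drop-out or loss to follow-up; 231 retained; then 1-5% not breastfeeding, leaving 219-228 for Phase 2.
- Retention: 308 x (1 - 0.10 - 0.15) = 308 x 0.75 = 231. This reproduces the plan. (The section also gives 324 as the total, but 324 x 0.75 = 243, so 231 comes from 308.)
- Exclusion for stillbirth or prematurity: 308 x 0.10 = 30.8, or 15.4 per group with equal arms. This reproduces the plan's figure of about 15.
- Non-breastfeeding: 231 x 0.95 = 219.5 and 231 x 0.99 = 228.7. With decimals dropped, these give the plan's 219 and 228.

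The last step matters most. Not breastfeeding is drop-out criterion (e), and the plan subtracts those participants from the number available to assess Phase 2 outcomes. Stillbirth, criterion (b), is also budgeted as an exclusion. So for two of the five criteria, meeting the criterion costs an analysed participant. In contrast, section 2.4.1 says explicitly that anthropometry and development data will continue for low-birth-weight or premature infants. It says nothing like this for the drop-out events.

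**3. How many are affected.** Expected loss before Phase 2 is 308 - 231 = 77 women (25%). About 31 of these are stillborn or premature births combined. The SAP does not split stillbirth from prematurity, and does not say whether preeclampsia and anomalies fall within the 15%. It gives no rates for them. The number of harm events that would go uncounted therefore cannot be derived.

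**The case against.** The live-born sentence names infants. On its ordinary reading, any infant who is analysed must be live-born, and no mother is excluded. It does not touch a woman with preeclampsia and a live birth, or a live-born infant with an anomaly. Drop-out is never defined as removal from analysis, and no sentence says that data up to the event are discarded. The diagnosis that triggers drop-out could itself be counted in an incidence rate. The figures in 2.4.2 are planning arithmetic, not an analysis-set rule: the same section budgets premature births as exclusions although 2.4.1 keeps those infants in growth data collection. Undesirable events go to the DSMB and Ethics Committee, and the plan commits to the CONSORT cluster extension. Definitions of morbidity and adverse events may be in the protocol, which is not at hand.

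Much of this stands. A reader might infer that the plan removes preeclampsia, stillbirth and anomalies from every comparison between arms, so that the trial could not show such harms. The SAP does not support that as a stated rule, except for stillbirth as an infant event. Nor does it support a claim that the remaining morbidity comparison is biased towards no difference. Selection on events after randomisation can shift that comparison either way.

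The objection does not remove the gap. Intention to treat is not stated for secondary outcomes. The DSMB route promises no table by arm, and the general reporting commitment fixes no denominator. The scope of a restriction on all analyses is for the SAP to set.

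**Conclusion.** The point holds as a wording fault that should be fixed. One rule is scoped too widely, and a second term has no stated analysis consequence. Followed literally, stillbirth leaves every planned analysis and mothers of stillborn infants may leave the maternal outcomes. Preeclampsia leads to drop-out with no statement that it is counted under outcome 9. No comparison of these events by arm is planned.

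The firm part is the omission of these events from the planned comparisons. That drop-out removes data is an inference from how section 2.4.2 treats stillbirth and non-breastfeeding. The size is unknown, since the SAP gives no rates for these events and none are assumed here.

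The live-born restriction itself is defensible for birth length and infant growth, and no sample size changes. The clinical handling of women who meet a drop-out criterion is not judged.

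**What to change.** In section 4.2:

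- Limit the live-born restriction to infant outcomes.
- State that maternal outcomes are analysed in all randomised women (those enrolled, by the arm of their village) with a measurement, whatever the pregnancy outcome.
- State that women and infants meeting a drop-out criterion contribute data up to and including that event, and that preeclampsia or eclampsia counts in outcome 9.
- Report pregnancy loss and stillbirth, preeclampsia or eclampsia, congenital anomaly and infant death by randomised group, as descriptive counts with confidence intervals. Use all randomised women as the denominator for maternal and pregnancy events, and name the denominator for infant events.

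A cross-reference in 2.4.1 should say that the drop-out list does not define the analysis set.

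The cost is a few sentences and one table. The listed events must already be recorded for the drop-out criteria to be applied. The drawback is that counts will be low and intervals wide, so the table will describe harms and not test for them.

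### As written, an infant measured at birth but not at 5 months drops out of both Phase 2 primary comparisons; a joint model of the two lengths would keep it

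*SAP*

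**What the plan says.** Section 4.2 gives one model: "Intervention groups will be compared using mixed effect regression models using cluster (village) as a random effect". It mentions no infant-level effect, visit term or arm-by-visit term.

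The outcomes are set in the same section: "Main outcomes for analyses for phase 1 are birth length", and "for phase 2 are attained and incremental linear growth at 5 months post-partum". Section 3.1 defines the growth outcome as "linear growth velocity of infants from birth to age 5 months".

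On who is analysed, section 4.2 says "Primary analyses will be by intention to treat" and "Only live born infants will be included in all analyses". It adds adjustment of Phase 2 for weight-for-age and breastfeeding practice where appropriate. The SAP contains no imputation or other missing-data rule.

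Section 2.4.2 allows for about 10% stillborn or premature births and for "drop-out or loss-to-follow-up of approximately 15" per cent. It then speaks of 231 participants retained and 219-228 available for Phase 2. Its Phase 2 calculation assumes "a within-person correlation of 0.73 and a design effect of 1.1 due to village clusters".

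**The concern.** Attained length and growth from birth each give one number per infant, and neither exists without the 5-month length. In a model with village as the named random effect, an infant lost after delivery has no outcome and is deleted. Yet its birth length is known, because that is the Phase 1 primary outcome. On the SAP's own correlation of 0.73, birth length also carries real information about the missing value.

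The stake is mainly possible bias, and secondarily some precision. The Phase 2 contrast would compare infants who stayed. If staying relates to birth length differently in the two arms, the contrast shifts. The intention-to-treat label does not say how infants without an outcome are handled.

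**Working it through.** **Inputs from the SAP.** Section 2.4.2: recruitment 308; about 10% stillborn or premature; about 15% drop-out or loss; 231 retained; 219-228 for Phase 2; SD 2.2; r = 0.73; design effect 1.1; difference 0.70; power 0.80; alpha 0.05 (two-sided assumed). The SD is read as 2.2 cm for length, as in Table 2.

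**The plan's own figure.** Per group, n = 2(1.96 + 0.842)² × variance / 0.70², rounded up and multiplied by 1.1.

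| Analysis | Variance | n | × 1.1, rounded up |
|---|---|---|---|
| 5-month length alone | 2.2² = 4.84 | 156 | 172 |
| Change from birth | 4.84 × 2(1 − 0.73) = 2.61 | 84 | 93 |
| Adjusted for birth length | 4.84 × (1 − 0.73²) = 2.26 | 73 | 81 |

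Only the last matches the stated 81 per group. The sample size thus appears to use birth length as a covariate, but section 4.2 does not name it as one.

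**How many infants.** 308 × 0.75 = 231, and 308 × 0.90 = 277.
- If the 231 all have a birth length, 231 − 228 = 3 to 231 − 219 = 12 are lost between the two comparisons.
- If all of the 15% leave after birth, 277 − 231 = 46, rising to 277 − 219 = 58 once infants who are not breastfed are also removed.

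The 277 follows the SAP's allowance, which takes out premature births.

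**Precision.** Let f be the fraction of infants with a birth length who lack a 5-month length. Relative to deleting them, the joint model has variance ratio
- attained length: 1 − r²f;
- growth: [(1 − r²) + (1 − r)²(1 − f)] / [2(1 − r)].

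| Case | f | Attained | Growth |
|---|---|---|---|
| 3 of 231 | 0.013 | 0.993 | 0.998 |
| 12 of 231 | 0.052 | 0.972 | 0.993 |
| 46 of 277 | 0.166 | 0.912 | 0.978 |
| 58 of 277 | 0.209 | 0.888 | 0.972 |

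With 219-228 analysed and infants without a 5-month length deleted, power is 0.89-0.91 for 1.0 cm in attained length and 0.86-0.88 for 0.70 cm in change.

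**Bias.** Assumptions: a true difference of 1 cm at birth and at 5 months, so no true growth difference; SD 2.2 cm at both; r = 0.73; log-odds of loss linear in birth length, with odds ratio 2 or 3 per SD shorter.

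Loss related to birth length in the placebo arm only: let m be the mean birth length of retained placebo infants, in SDs above that of all placebo infants. It was found by numerical integration, with the average placebo loss fixed at the stated rate. The deleted-case estimate of attained length is 1 − 2.2 × 0.73 × m = 1 − 1.606m. The false growth difference is 2.2 × (1 − 0.73) × m = 0.594m.

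| Placebo loss | Odds ratio | m | Attained (cm) | False growth (cm) |
|---|---|---|---|---|
| 15% | 2 | 0.098 | 0.84 | 0.06 |
| 15% | 3 | 0.142 | 0.77 | 0.08 |
| 5% | 2 | 0.034 | 0.95 | 0.02 |
| 5% | 3 | 0.051 | 0.92 | 0.03 |

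Loss related to birth length alike in both arms: the estimate lies between about 0.93 and 0.98 cm over the same loss rates and odds ratios. With no difference at birth, this pattern gives essentially no bias.

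Regressing 5-month length on birth length within arm and standardising to all births, which is what the joint model does, returns about 1.00 cm in every scenario.

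**The case against.** *One record per infant is an inference.* Section 4.2 names village as a random effect and does not say that it is the only one. This is true, but no other coherent reading is on offer. Two lengths per infant with village alone would ignore the correlation that section 2.4.2 assumes.

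*The sample size implies adjustment for birth length, so loss related to it is already conditioned on.* That covariate is not named in section 4.2. Birth length also follows randomisation, so conditioning on it changes the question. With 1 cm differences at both times, the adjusted contrast would be 1 − 0.73 × 1 = 0.27 cm, which is neither attained length nor growth.

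*Few infants may be affected.* This stands. A reader might infer that 15% are lost after birth, but the documents do not say so. Follow-up starts at 8-14 weeks' gestation, and section 2.4.2 can be read as 231 reaching Phase 1 and only 1-5% leaving afterwards. That later loss is failure to breastfeed, which section 2.4.1 lists as a drop-out criterion. Those infants leave by rule and not through the model.

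*Differential loss is unlikely in a double-blind trial with identical-looking crackers.* This is a fair point, and the SAP gives no evidence of differential loss. It follows that one should not claim the plan is valid only if leaving is unrelated to birth length: similar dependence in both arms does little harm.

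**Conclusion.** The point holds as a gap in the stated analysis. Followed as written, section 4.2 removes from both Phase 2 primary comparisons every live-born infant with a birth length and no 5-month length, and no rule says otherwise. The number ranges from 3-12 to about 46-58, depending on when the losses fall.

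The gain in precision is modest, and the documents do not support a claim that the trial is underpowered. Material bias needs loss that depends on birth length differently by arm. The bias figures are illustrations under assumed loss patterns, not predictions. The change is worth making because it is cheap and rests on a weaker assumption than deletion; the plan as it stands is not shown to give a wrong answer.

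**What to change.** State in section 4.2 that the primary Phase 2 analysis is a repeated-measures mixed model with:
- birth length and 5-month length as outcomes;
- fixed effects for arm, visit and arm by visit;
- a village random effect and an unstructured within-infant covariance;
- arm means at birth left free, because birth length is measured after randomisation;
- all live-born infants with a birth length included.

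The arm contrast at 5 months gives attained length. The change in the arm contrast from birth to 5 months gives growth.

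Move the adjustment for weight-for-age and breastfeeding practice to a secondary analysis. Infants who leave have no 5-month values of these, so keeping that adjustment in the primary model would delete them again.

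The model assumes that loss is explained by arm and observed lengths. Add a simple sensitivity analysis for departures, for example shifting the unobserved 5-month lengths by arm over a stated range.

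The cost is SAP wording and some programming. Both lengths are already planned measurements, so nothing further need be collected.
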